JUVÉDERM VOLITE XC injectable gel will be administered using a 32 G 1/2" or a 32 G 3/16" needle in multiple microdepot injections across both cheeks. At initial and repeat (if performed) treatments, volume is not to exceed a total of 4 mL for both cheeks. At optional touch-up procedure, volume is not to exceed 2 mL for both cheeks. Needle length selection, total injection volume, and injection spacing will be determined by the TI.
DURATION OF STUDY: Treatment group: up to 1 month for screening, up to 1 month for treatment, 6 months of follow-up, and 4 months of follow-up after optional repeat treatment. Control group: up to 1 month for screening and 1 month of follow-up; up to 1 month for treatment and 6 months of follow-up after optional treatment.
OBJECTIVES: The objective of this study is to evaluate the safety and effectiveness of JUVÉDERM VOLITE XC injectable gel for the improvement in cheek skin smoothness.
KEY ENDPOINTS: 
 Primary: ACSS responder status at Month 1 Secondary: Change from baseline to Month 1 on FACE-Q Satisfaction with Skin questionnaire Secondary: AFLS responder status at Month 1 Safety: FACE- Recovery Early Life Impact questionnaire, procedural pain, ISRs from 30-day e-diaries, AIs, Snellen visual acuity, confrontation visual fields, and ocular motility
OVERALL STUDY DESIGN: 
 Randomized, controlled, parallel-design Single-blind: EI s are blinded; TIs and subjects are not blinded Treatment group subjects receive initial treatment and optional touch-up treatment at 30 days if needed to achieve optimal correction. Follow-up visits are 3 days after each treatment (safety only) and at Months 1, 2, 4, and 6 after last treatment. Subjects exit the study at Month 6 or receive repeat treatment and are followed at Day 3 and Months 1 and 4 after repeat treatment. Control group subjects are followed for 1 month after randomization (no-treatment control period) and then either exit the study or receive optional treatment (initial and touch-up, if needed) in the delayed treatment period. Follow-up visits are 3 days after each treatment (safety only) and at Months 1, 2, 4, and 6 after last treatment. Subjects exit the study at Month 6.

DIAGNOSIS AND CRITERIA FOR INCLUSION/EXCLUSION:

Adults seeking improvement in cheek skin smoothness

INCLUSION:

1. Age 22 or over and in good general health
2. Has an ACSS score of 2 for both cheeks or 3 for both cheeks on the 5-point Allergan cheek smoothness photonumeric scale (range: 0 to 4), as judged live by the EI
OR
has Fitzpatrick skin phototype V or VI and has an ACSS score of 1, 2, or 3 on both cheeks (the cheeks do not need to have the same score), as judged live by the EI (Fitzpatrick V/VI safety cohort)
3. Has a FACE-Q Satisfaction with Skin Questionnaire sum score of 39 or less (sum score of 39 is equivalent to Rasch-transformed score of 69) unless enrolled as part of the Fitzpatrick V/VI safety cohort
4. Ability to follow study instructions and likely to complete all required visits
5. Written informed consent and data privacy consent have been obtained

EXCLUSION:

1. Requires more than 6 mL of product for optimal correction of both cheeks based on the TI's clinical judgment
2. Has undergone tissue augmentation with dermal fillers including HA, calcium hydroxylapatite, autologous fat, mesotherapy, or other cosmetic procedures (eg, face-lift, laser, photomodulation, intense pulsed light, radiofrequency, dermabrasion, chemical peel, or other ablative procedures) in the face within 12 months before screening or is planning to undergo any such treatment during the study
3. Has received any crosslinked HA filler in any anatomic area within 12 months of screening
4. Has undergone treatment with botulinum toxin in the cheek area (including crow's feet) within 6 months of screening or is planning to undergo such treatment during the study
5. Has ever received semipermanent fillers or permanent facial implants (eg, poly-L-lactic acid, polymethylmethacrylate, silicone, expanded polytetrafluoroethylene) anywhere in the face or is planning to be implanted with any of these products at any time during the study
6. Has facial tattoos, piercings, pigmentation, hair (ie, beard, mustache), or past trauma that would interfere with the visualization of the face for the effectiveness assessments
7. Has undergone a dental procedure within 6 weeks before treatment or plans to undergo a dental procedure (other than prophylaxis or dental fillings) during the course of the study
8. Has a tendency to develop hypertrophic scarring
9. Has a history of allergy to lidocaine, HA products, and/or to gram-positive bacterial proteins as HA is produced by *Streptococcus*-type bacteria, or is planning to undergo desensitization therapy during the term of the study
10. Has a history of anaphylactic shock
11. Has current cutaneous inflammatory or infectious processes (eg, acne, herpes), abscess, an unhealed wound, or a cancerous or precancerous lesion on the face (injection may be delayed to allow subjects with a history of recurrent oral herpes to take prophylactic antiviral/herpes medication for 2 days)
12. Is on an ongoing regimen of anticoagulation therapy (eg, warfarin) or is known to have a coagulation disorder
13. Is on an ongoing regimen of medications (eg, aspirin, ibuprofen) or other substances (eg, herbal supplements with garlic, ginkgo biloba, or ginseng) known to increase coagulation time within 10 days of undergoing study device injection (study device injection may be delayed as necessary to accommodate this 10-day washout period)
14. Has active autoimmune disease
15. Has received any investigational product within 30 days before enrollment or is planning to participate in another investigation during the course of this study
16. Has begun using any over-the-counter or prescription, oral or topical, anti-wrinkle products on the face within 30 days before enrollment or is planning to begin using such products during the study (subjects who have been on a regimen of such products for at least 30 days are eligible for the study if they intend to continue their regimen throughout the study)

17. Females who are pregnant, nursing, or planning a pregnancy during the study
18. Is an employee (or a relative of an employee) of the PI/TI/EI/site, Allergan, or representative of Allergan
19. Has a condition or is in a situation which, in the TI's opinion, may put the subject at significant risk, may confound the study results, or may interfere significantly with the subject's participation in the study

STATISTICAL METHODS:**Sample Size Calculation:**

A sample size of 112 subjects in the treatment group and 56 subjects in the control group will provide 99.9% power to detect a difference of at least 40% in the responder rates on ACSS between the groups, based on a 2-sided Fisher's exact test at the 5% level. The treatment group is assumed to have at least an 80% responder rate at Month 1, and the control group is assumed to have at most a 40% responder rate. The assumptions of responder rates are estimated from Allergan study V12-001.

At least 135 subjects with a baseline AFLS score of 2 on both cheeks or 3 on both cheeks are expected to enroll. The number of subjects with baseline AFLS score of 0, 1, or 4 on either cheek, or 2 on one cheek and 3 on the other cheek is not expected to exceed 75. Assuming at least 65% of subjects will have baseline AFLS score of 2 on both cheeks or 3 on both cheeks, 72 subjects in treatment group and 36 subjects in control group will provide 94.4% power to detect a difference of at least 35% in the responder rates on AFLS between the treatment groups, based on a 2-sided Fisher's exact test at the 5% level. The treatment group is assumed to have at least an 80% responder rate at Month 1, and the control group is assumed to have at most a 45% responder rate. The assumptions of responder rates are estimated from Allergan study V12-001.

Accounting for subject attrition of 20% during the study, 210 subjects will be randomized at a 2:1 ratio to treatment group and control group. Randomization will be within each study site.

Assuming 119 subjects from the treatment group and 28 subjects from the control group will be treated, a total of 147 treated subjects will provide 95% power to detect an AE related to treatment with an incidence rate of 2% in the population using a 1-sided exact binomial test at the 2.5% level. The safety calculation used an inequality test for 1 proportion.

Effectiveness:

The primary effectiveness measure is the EI's assessment of cheek skin smoothness using the ACSS. The primary effectiveness analysis is the ACSS responder rate at Month 1. A responder is defined as a subject who shows at least a 1-point improvement from baseline on the ACSS on both cheeks. The responder rate and corresponding 95% confidence interval will be summarized. A 2-sided, Fisher's exact test at the 5% level will be used to test whether the ACSS responder rate at Month 1 in the treatment group is significantly greater than that in the control group at Month 1 in the control period. The primary effectiveness endpoint will be met if the responder rate for the treatment group is statistically greater than that for the control group at Month 1.

The secondary effectiveness variables are 1) subject responses on the FACE-Q Satisfaction with Skin questionnaire, and 2) EI's assessment of fine lines on the cheeks on the AFLS. The secondary effectiveness analyses include change from baseline in FACE-Q scale score at Month 1 and the AFLS responder rate at Month 1. The responses to the 12 FACE-Q items will be summed and converted to a scale score that ranges from 0 to 100 (higher score indicates more satisfaction) using the algorithm developed by the FACE-Q scale developers. An AFLS responder is defined as a subject who shows at least a 1-point improvement from baseline on the AFLS scale on both cheeks. The AFLS responder rate will be analyzed in the same manner as the ACSS responder rate. Only subjects with baseline AFLS score of 2 on both cheeks or 3 on both cheeks will be included in the analysis.

Safety:

AEs will be summarized by primary system organ class, preferred term, and severity. Treatment-related AEs, AEs leading to discontinuation, serious adverse events, and deaths will be listed or tabulated. ISRs will be summarized using descriptive statistics, by symptom, maximum reported severity, and duration for initial,

touch-up, and repeat treatments, separately. Frequency distributions or descriptive summaries of procedural pain and results of FACE-Q Recovery Early Life Impact questionnaire will be provided. Snellen visual acuity, confrontation visual fields, and ocular motility assessments performed by the TI (or designee) will be summarized descriptively.

2. Schedule of Activities

In general, study procedures may be done in sequence as listed in the below tables, but the sequence may be modified based on each site's usual and customary clinic flow. However, there are certain procedures that must be performed before others, and that sequence cannot be altered: inclusion/exclusion criteria including ACSS and FACE-Q Satisfaction with Skin questionnaire **must be completed on the day of Randomization and must be completed before Randomization occurs**). Where possible, subject questionnaires are to be completed prior to other assessments at each visit.

Table 2-1 Screening Visit Procedures: All Subjects

Procedure	Screening
	Visit Window
	-30 Days
Consent/ Authorization	X
Subject demographics	X
Height, weight, and vital signs ^a	X
Fitzpatrick skin phototype and sun exposure history	X
Smoking history	X
Cosmetic, medical, surgical, and dental history	X
Inclusion/Exclusion criteria (TI, EI, Subject). Exclude ACSS assessment and FACE-Q Satisfaction with Skin assessment if Randomization does not occur during this visit^b	X
Urine pregnancy test ^c	X

^a Includes blood pressure (systolic and diastolic) while subject is seated, pulse rate, and temperature.

^b ACSS assessment by TI and FACE-Q Satisfaction with Skin assessment by Subject are to be performed only at Randomization visit. Note: it is possible the subject will subsequently be deemed ineligible for the study once these assessments are performed at the Randomization visit.

^c For female subjects of childbearing potential; administered and confirmed negative. A female subject is not considered of childbearing potential if she has been postmenopausal for at least 1 year or does not have a uterus at the time of study entry.

Table 2-2 Treatment Group Procedures

^a Randomization must occur within 30 days of screening; screening visit and randomization visit can occur on the same day if subjects do not require washout. If screening and randomization visits occur on the same day, inclusion/exclusion criteria and urine pregnancy testing need not be repeated.

b The TI may perform a touch-up treatment, 30 days after initial treatment, if the TI determines that optimal correction was not achieved with initial treatment. If no touch-up treatment is performed, Day 30 visit becomes Month 1 visit.

c Study exit visit is at Month 6 for subjects not receiving repeat treatment. If repeat treatment is performed, Month 6 will be repeat treatment visit, and exit visit will be at Month 4 after repeat treatment.

^d For female subjects of childbearing potential; administered and confirmed negative prior to randomization/treatment. A female subject is not considered of childbearing potential if she has been postmenopausal for at least 1 year or does not have a uterus at the time of study entry.

e Randomization and initial treatment for the treatment group must occur on the same day.

On treatment days, vision assessments will be performed before treatment and approximately 30 minutes after treatment.

The treatment procedure is to be performed after all effectiveness assessments and 2D facial imaging.

h The 30-day daily safety e-diaries are to be completed following each treatment starting on the day of treatment and are considered complete if all days are completed until the Day 30/Month 1 visit.

Table 2-3 Control Group Procedures (No-Treatment Period)

Procedure	Randomization ^a	Month 1 Study Exit visit
Visit Window (Days)		-2/+7
Urine pregnancy test ^b	X	
Inclusion/Exclusion criteria (TI, EI, Subject)	X	
FACE-Q Satisfaction with Skin questionnaire (Subject)	X	X
FACE-Q Appraisal of Lines-Overall questionnaire (Subject)	X	X
ACSS (EI)	X	X
AFLS (EI)	X	X
Skin hydration (EI)	X	X
2D facial imaging	X	X
Randomization	X	
Weight measurement		X
Concomitant medications, procedures, treatments	Continuous Monitoring	
Adverse events	Continuous Monitoring	

^a Randomization must occur within 30 days of screening; screening visit and randomization visit can occur on the same day if subjects do not require washout. If screening and randomization visits occur on the same day, inclusion/exclusion criteria and urine pregnancy testing need not be repeated.

^b For female subjects of childbearing potential; administered and confirmed negative prior to randomization. A female subject is not considered of childbearing potential if she has been postmenopausal for at least 1 year or does not have a uterus at the time of study entry.

Table 2-4 Control Group Procedures (Delayed Treatment Period)

Procedure	Initial Tx ^a	Day 3 after Initial Tx	Touch-up Tx Day 30 ^b	Day 3 after Touch-up Tx	Month 1	Month 2	Month 4	Month 6 Study Exit Visit
Visit Window (Days)	+7	+2	-2/+7	± 2	-2/+7	±7	±7	±7
Urine pregnancy test ^c	X		X					X
Snellen visual acuity (TI or designee)	X ^d	X	X ^d	X	X			
Confrontational visual fields (TI or designee)	X ^d	X	X ^d	X	X			
Ocular motility (TI or designee)	X ^d	X	X ^d	X	X			
Treatment procedure ^e	X		X					
Procedural pain	X							
Safety e-diary ^f (Subject)	X		X					
FACE-Q Recovery Early Life Impact questionnaire (Subject)		X						
2D facial imaging		X	X		X	X	X	X
FACE-Q Satisfaction with Skin questionnaire (Subject)			X		X	X	X	X
FACE-Q Appraisal of Lines-Overall questionnaire (Subject)			X		X	X	X	X
Natural look and feel assessment (Subject)			X		X	X	X	X
GAIS (Subject)			X		X	X	X	X
ACSS (EI)			X		X	X	X	X
AFLS (EI)			X		X	X	X	X
Skin hydration (EI)			X		X	X	X	X
Weight measurement								X
Concomitant medications, procedures, treatments					Continuous Monitoring			
Adverse events					Continuous Monitoring			

^a Initial treatment for the control group is offered only after completion of 1 month of no-treatment control period.

^b The TI may perform a touch-up treatment, 30 days after initial treatment, if the TI determines that optimal correction was not achieved with initial treatment. If no touch-up treatment is performed, Day 30 visit becomes Month 1 visit.

^c For female subjects of childbearing potential; administered and confirmed negative prior to treatment. A female subject is not considered of childbearing potential if she has been postmenopausal for at least 1 year or does not have a uterus at the time of study entry.

^d On treatment days, vision assessments will be performed before treatment and approximately 30 minutes after treatment.

^e The treatment procedure is to be performed after all effectiveness assessments and 2D facial imaging.

^f The 30-day daily safety e-diaries are to be completed following each treatment starting on the day of treatment and are considered complete if all days are completed until the Day 30/Month 1 visit.

3. Introduction

JUVÉDERM VOLITE™ XC (with lidocaine) is an HA-based injectable gel dermal filler for improvement in facial skin smoothness to meet an unmet need for this indication.

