5.1 Overall Design

[figure not shown]
This is a multicenter, evaluator-blind, controlled, parallel-design, prospective study of adults seeking improvement in cheek skin smoothness. Up to 20 investigational sites will enroll and follow subjects who meet the study criteria according to the study design in [Figure 5-1](#). Each site will have a PI who is responsible for the overall conduct of the study at that site and may also be the TI. The TI performs all study treatments, and the blinded EI evaluates ACSS, AFLS, and skin hydration measurements.

The study will span a total of approximately 20 months: an estimated 9 months for recruitment and 11 months for follow-up. For the treatment group, each subject's participation will encompass up to 30 days of treatment and up to 10 months of follow-up (6 months for those choosing not to receive repeat treatment at Month 6). For the control group, each subject's participation will encompass 1 month; for control subjects who opt to receive treatment, the treatment period will be up to 30 days, and the follow-up period will be up to 6 months.

Treatment group subjects receive initial treatment and optional touch-up treatment at 30 days if needed to achieve optimal correction. Follow-up visits are 3 days after each treatment (safety only) and at Months 1, 2, 4, and 6 after last treatment. Subjects exit the study at Month 6 or receive repeat treatment and are followed at Day 3 and Months 1 and 4 after repeat treatment. Control group subjects are followed for 1 month after randomization (no-treatment control period) and then either exit the study or receive optional treatment (initial and touch-up, if needed) in the delayed treatment period. Post-treatment follow-up visits are 3 days after each treatment and at Months 1, 2, 4, and 6 after last treatment.

To ensure adequate enrollment of subjects with Fitzpatrick skin phototype V and VI, up to 10 subjects may be enrolled in the Fitzpatrick V/VI safety cohort with less stringent inclusion criteria (see [Section 6.1](#)) and followed for safety only.

Figure 5-1 Study Design

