7.5 Blinding/Masking

The EIs will be blinded to treatment and will not be present during the injection procedures.

The PIs/TIs, study coordinators, and subjects will not be blinded to treatment, and they will secure the randomization and other records (eg, records of study treatments and prior study assessments) from potential discovery by the blinded EI. The TIs will not discuss the randomized treatment assignments with or in the presence of the EIs.

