9.3 Effectiveness Assessments

9.3.1 Primary Effectiveness Measure

[figure not shown]
The primary effectiveness measure is the EI's assessment of cheek skin smoothness using the ACSS scale described in Table 9-1. The anatomic area to be rated for skin smoothness is defined as from the oral commissure to the preauricular cheek and from the zygomatic arch to the mandible (Figure 9-1).

The ACSS is a validated 5-point ordinal scale developed by Allergan to grade the severity of skin smoothness on the cheeks. The ACSS contains a morphed subject photograph showing all 5 severities of cheek smoothness as well as photographs of subjects representing different Fitzpatrick skin types, race categories, both sexes, and all severities of skin smoothness. Prior to initiating enrollment at their site, all investigators (TIs and EIs) will be trained in the use of the ACSS and demonstrate substantial inter- and intra-rater agreement.

Table 9-1 Allergan Cheek Smoothness Scale

Score	Grade	Description
0	None	Smooth visual skin texture
1	Minimal	Slightly coarse and uneven visual skin texture
2	Moderate	Moderately coarse and uneven visual skin texture; may have early elastosis
3	Severe	Severely coarse visual skin texture, crosshatched fine lines; may have some elastosis
4	Extreme	Extremely coarse visual skin texture, crosshatched deep creases; extreme elastosis

Figure 9-1 Assessment Area for the Allergan Cheek Smoothness Scale

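### Table 2-1 footnote b names the TI as ACSS rater at the Randomization visit, where the inclusion criterion, Table 2-3, Section 5.1 and the primary endpoint name the EI

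*Protocol*

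**What the plan says.** Footnote b to Table 2-1 (protocol Section 2) states that "ACSS assessment by TI and FACE-Q Satisfaction with Skin assessment by Subject are to be performed only at Randomization visit".

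The other places that assign this rating name the EI:

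- Synopsis, inclusion criterion 2: eligibility is set on the "photonumeric scale (range: 0 to 4), as judged live by the EI".
- Section 5.1: "The TI performs all study treatments, and the blinded EI evaluates ACSS, AFLS, and skin hydration measurements".
- Table 2-3 (control group, no-treatment period): the ACSS row is marked EI at both Randomization and Month 1.
- Synopsis (Effectiveness), Sections 9.3.1 and 10.3.1.2, and SAP Sections 2 and 5.3.1: the primary measure is the EI's rating.

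On timing, the introduction to Section 2 says that the eligibility assessments, including the ACSS, "must be completed on the day of Randomization and must be completed before Randomization occurs".

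SAP 5.1 takes as baseline the latest available value up to the later of randomization and first treatment in the control period. It does not say whose rating that must be.

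**The concern.** Footnote b is an instruction to sites. The eligibility row to which it is attached, "Inclusion/Exclusion criteria (TI, EI, Subject"), lists three parties without saying which of them scores the ACSS. The footnote fills that gap, and fills it with the TI. A site could follow it in good faith, because Section 9.3.1 says that "all investigators (TIs and EIs) will be trained in the use of the ACSS".

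The score does two jobs. It decides entry to the main cohort, which needs grade 2 on both cheeks or grade 3 on both cheeks. It also anchors the primary endpoint, where one grade on each cheek separates a responder from a non-responder. If the TI supplies it and the EI supplies Month 1, a one-grade difference between raters can create or remove a response with no change in the skin. Section 9 recommends, but does not require, that one EI follow each subject.

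**Working it through.** **1. The texts side by side (ACSS at the Randomization visit)**

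| Place | Rater |
|---|---|
| Protocol Table 2-1, footnote b | TI |
| Protocol synopsis, inclusion criterion 2 | EI |
| Protocol Table 2-3 | EI |
| Protocol Section 5.1 | EI |
| Primary measure: protocol 9.3.1 and 10.3.1.2; SAP 2 and 5.3.1 | EI |
| Eligibility rows of Tables 2-1 and 2-3 | TI, EI and subject listed; ACSS rater not specified |
| SAP 5.1 baseline rule | not stated |

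The footnote stands alone and cannot be read so as to agree with the rest. The body of Table 2-2 (treatment group) is not legible in the copy available and should be checked.

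**2. What a crossed pair of raters does**

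- The EI would score 1 on both cheeks; the TI scores 2 on both. The subject enters the main cohort without meeting the EI criterion. An unchanged EI score of 1 at Month 1 then counts as a response, in either arm.
- The EI would score 3 on both cheeks; the TI scores 2 on both. A true improvement to an EI score of 2 at Month 1 is lost.

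**3. The plan's own figure**

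Inputs from the synopsis and SAP Section 3: 112 and 56 subjects, 80% vs 40%, 2-sided Fisher's exact test at 5%. Exact enumeration over the two binomials gives power 0.9991, which agrees with the stated 99.9%. The number randomized also agrees: (112 + 56)/0.80 = 210.

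**4. Illustration of size (assumed rates)**

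Let u be the share of true non-responders turned into responders by a TI baseline that is too high. Let d be the share of true responders lost through one that is too low. Take both as equal in the two arms, because the rating precedes allocation. Then

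p′ = p(1 − d) + (1 − p)u, and the difference becomes (0.80 − 0.40)(1 − u − d).

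For u = 0.10, d = 0: 0.80 + 0.10 × 0.20 = 0.82; 0.40 + 0.10 × 0.60 = 0.46; difference 0.36.

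For u = 0, d = 0.10: 0.80 × 0.90 = 0.72; 0.40 × 0.90 = 0.36; difference 0.36.

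| u | d | Rates | Difference | Exact Fisher power, 112/56 |
|---|---|---|---|---|
| 0 | 0 | 80% vs 40% | 40 points | 99.9% |
| 5% | 0 | 81% vs 43% | 38 points | 99.8% |
| 10% | 0 | 82% vs 46% | 36 points | 99.7% |
| 20% | 0 | 84% vs 52% | 32 points | 99.0% |
| 0 | 10% | 72% vs 36% | 36 points | 99.4% |
| 10% | 10% | 74% vs 42% | 32 points | 97.6% |
| 20% | 20% | 68% vs 44% | 24 points | 82.6% |

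If the true rates are equal, p′ is the same in both arms, so this error does not by itself create a false difference.

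The model is simple. It supposes that the stated share is affected across the whole trial, that each affected subject changes status on both cheeks, and that the enrolled population stays the same.

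**The case against.** The strongest reply is that this is one stray word. The EI is the rater everywhere else, footnote b belongs to the screening table, and its purpose is timing. TI and EI differ by one letter, and the available text has other reading errors, so the approved protocol should be checked. TI training on the scale does not show that TIs rate for the study: Section 7.2 lets the TI consult the EI's scores when deciding on touch-up. A site using a TI score for entry would depart from inclusion criterion 2. The SAP baseline rule is a general timing rule, and SAP 2 and 5.3.1 already tie the endpoint to the EI. Most of this stands. It makes a drafting slip the likeliest explanation and the SAP clause a safeguard only. It does not make the footnote agree with the other text.

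A reader might infer more than the documents support:

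- **That an unblinded rater biases baseline by arm.** Section 7.5 does say that "The PIs/TIs, study coordinators, and subjects will not be blinded to treatment". But the rating comes before randomization, when no rater knows the allocation. In the model above the error shrinks a true difference and does not favour the product.
- **That the TI would score up to secure entry.** No passage gives the TI such a motive, and a higher score does not always help: grade 4 is ineligible.
- **That 10%, or any other rate, is the expected misrating.** The documents give no agreement figure. They require both roles to show substantial agreement within and between raters.

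**Conclusion.** The inconsistency is real and should be corrected. Footnote b assigns to the TI a score that the rest of the plan assigns to the EI, and that score both decides eligibility and serves as the primary baseline. The possible harm is rater-disagreement error in both arms and some subjects enrolled without meeting the EI-judged criterion. It arises only if sites acted on the footnote.

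The size cannot be computed from the documents. Little effect on power is expected: in the illustration power stays at 97% or more unless about a fifth of subjects are misclassified in each direction throughout the trial. What is at stake is the size of the effect estimate, the eligibility of individual subjects, and the description of the endpoint as an EI measure from baseline to Month 1.

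**What to change.** Change the rater in Table 2-1 footnote b from TI to EI, in agreement with inclusion criterion 2, Table 2-3 and Section 5.1, and confirm that Table 2-2 names the EI as well.

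As an optional safeguard, add a sentence to SAP 5.1 that ACSS baseline and follow-up values are taken only from EI ratings, consistent with SAP 2 and 5.3.1. If subjects were enrolled under the current footnote, check from source records who made each baseline ACSS rating.

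The cost is one word in the protocol, one clause in the SAP and, where it applies, a records check. The design, sample size and analysis method do not change.
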